1 STUDY INFORMATION

1.1 Full/Long Title of the Study

The benefits of adopting WYSA therapeutics for patients, clinicians, services and the wider health care system.

1.2 Short Study Title / Acronym

Evaluation of Wysa Therapeutics

1.3 Protocol Version Number(s) and Date(s)

1.0 Initial draft

5th November 2022 25th November 2023

1.1 Revised Protocol

1.4 Research Reference Numbers

IRAS Number:	320441
SPONSORS Number (if applicable):	
GRANT Number (If applicable):	N/A

4 ABBREVIATIONS AND KEY TERMS

Table 2. Abbreviations

Abbreviation / Key Term	Full Phrase / Definition
A&E	Accident and Emergency (Emergency department)
AI	Artificial Intelligence
ΑΡΙ	Application Programming Interface
СВТ	Cognitive Behavioural Therapy
сСВТ	computerised Cognitive Behavioural Therapy
DPA 2018	Data Protection Act 2018
EPR	Electronic Patient Record
GAD-7	General Anxiety Disorder questionnaire
GDPR	General Data Protection Regulation
GP	General Practitioner
HRA	Health Research Authority
NHS talking therapies	Improving Access to Psychological Therapies
ICMJE	International Committee of Medical Journal Editors
IRAS	Integrated Research Application System
NHS	National Health Service
NIHR	National Institute for Health Research
PHQ-9	Patient Health Questionnaire
РРІ	Patient and Public Involvement
RCT	Randomised controlled trial
REC	Research Ethics Committee
SWIFT	Structured What-IF Technique (prospective hazards analysis method)
WSAS	Work and Social Adjustment Scale

5 STUDY SUMMARY

Table 3. Study Summary

Study Title	The benefits of adopting WYSA therapeutics for patients, clinicians, services and the wider health care system.	
Short title	An evaluation of Wysa therapeutics	
Study Design	The study proposed is a real world quantitative evaluation to investigate the impact of Wysa therapeutics on clinical outcomes, and the experience of using the products in people with mild to moderate common mental health disorders. Outcome measures will include client satisfaction questionnaires and PHQ9 and GAD7 scores, as well as clinical and/or administrative time savings.	
Study Participants	The target population of the will include individuals over the age of 16 years who are referred, or self-refer, to Improving Access to Psychological Therapies programme (NHS talking therapies) for mental health support.	
Planned Size of Sample	The planned sample size is 100 individuals from 5 provider sites, two run by Dorset University Healthcare NHS Foundation Trust and three run by Lanchashire and South Cumbria NHS Foundation Trust.	
Follow up duration	N/A	
Planned Study Period	The study will last 18 months which includes three months of evaluation refinement, ethical approval, technical integration and testing. A further three months will be required for analysis of some secondary outcomes and preparation for dissemination.	
Research Question/Aim(s)	 The study aims are as follows: 1. To establish real-world evidence of the effectiveness of Wysa as a referral and triage tool. 2. To establish the impact of Wysa as a self help mental health support tool for patients waiting for treatment. 3. To establish the effectiveness of therapist enabled Wysa cCBT interventions on mental health outcomes. 4. To evaluate user experience of the range of Wysa therapeutics. 5. To establish if the adoption of Wysa therapeutics results in any service related efficiencies, for example clinical or administrative time savings. 	

The main research question is: How do the range of Wysa therapeutic tools benefit patients, clinicians, services and the wider health care system?
health care system?

5.1 Roles and Responsibilities of Study Management Committees/Groups and Individuals

A study steering board composed of the Chief Investigator, Principal Investigators, Co-Investigators, and Wysa's Adult Clinical Lead will meet every two months to review progress against the protocol to provide study governance and oversight.

6 STUDY FLOW CHART

Wysa is delivered as a standalone system that patients download directly onto their personal device. Wysa will be made available to patients as a self referral and clinical triage tool, and further along the care pathway will provide a range of therapist enabled computerised CBT programmes.

This study will conduct a quantitative feasibility review of Wysa as an AI therapeutic support tool across a typical care pathway in adult NHS talking therapies services. The study will take place in a collaborating NHS service utilising Wysa as an offer for all patients who have a suitable digital device.

Wysa's suite of products can be utilised at four key points in the care pathway:

- 1. Referral
- 2. Waitlist
- 3. NHS talking therapies step 2 intervention
- 4. Post discharge

The study will compare data from patients who use Wysa throughout their NHS talking therapies journey, or for at least a part of their journey, with those who do not.

Following self-referral (either using the Wysa electronic triage tool or another method such as self referral portal or email) or professional referral, the individual is provided access to the Wysa app via a download link. The patient can then use the app for support whilst waiting for their next contact with the service. Where the clinician has identified that a Wysa cCBT programme is an appropriate treatment intervention, this will be prescribed via an additional download link.

Wysa's Triage tool collects demographic and clinical patient related information via the AI chatbot. This tool will support patients to complete a referral to NHS talking therapies services, allowing the service to collect the data (via an API to their EPR system) required for a referral to be opened and a clinician to make a decision about the patient's care. Here we will review predetermined data points to understand how patients engage with the e-triage and the types of patients who utilise the tool. We will also compare the time taken for the clinician to reach a clinical outcome decision when the Wysa e-triage is completed with the time taken when a standard assessment is undertaken.

From here the patient will be offered the opportunity to download the Wysa app as a waitlist support tool until they are offered an intervention. The Wysa app includes over 150 self care tools, conversational AI and daily check-ins and reminders via push notifications. We will analyse data collected from within the app to understand app usage and any effect use of the app may have on mental wellbeing markers during the wait period.

Patients who are then offered Wysa's cCBT by their assessing clinician will have access to diagnosis specific weekly web or app based programmes including psychoeducational videos and CBT conversational techniques, as well as periodic reviews by an NHS talking therapies clinician through a communication dashboard called the Therapist Companion, which is also fully integrated into the service EPR system. We will report on changes in clinical outcome measures and engagement metrics to understand the efficacy of these cCBT programmes.

For all patients using Wysa within the service there is a built in SOS response. Wysa has three pathways to crisis alert and response:

- Patients are able to trigger crisis help by selecting the 'SOS' button on the app.

Version number 1.1 - 25th November 2023

- Crisis response will be triggered by responses to PHQ9 question 9
- Crisis response will be triggered when risk language is used (and confirmed by the chatbot) within free text.

When Wysa or the user triggers the crisis response pathway, users will be offered to complete a safety plan, engage in grounding exercises, and be provided with local or national crisis helplines. We will collect data including the number of times that the Wysa SOS response is triggered, the number of false positives identified by the AI, and SOS tool usage.

After patients have been discharged, Wysa can also be used as a support/ relapse prevention tool. All participants will have access to the AI Chatbot and self tools for 12 months from onboarding.

[figure not shown]

Figure 1. Current NHS talking therapies care pathway flows including Wysa therapeutics.

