7.4 Aims and Objectives

The primary aim of this project is to understand the clinical benefits of Wysa AI therapeutics for patients.

The Primary objective of this study is as follows:

- Do Wysa therapeutics (e-triage, self-help tools & conversational care; guided cCBT), when deployed at referral, waitlist, and intervention, improve clinical outcomes?

The Secondary objectives of this study are to explore:

- Do Wysa therapeutics improve service referral rates and/or reduce drop outs or DNAs?
- Do Wysa therapeutics improve patients' quality of life?
- Do Wysa therapeutics have an impact on waitlist numbers or other service related resources?

[figure not shown]

Figure 2: Wisconsin Logic Diagram

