8.1.1 Timeline

The study will last for 10 months: 3 months of evaluation, refinement and technical integration, 6 months of data collection (the total time period for each participant journey will be approximately 20 weeks, thus allowing a 4 week onboarding window), and 1 month of post-evaluation analysis and preparation for dissemination.

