8.2 Study Context

8.2.1 Participants

The target population of the study will include patients who are 16+ who are referred, or self-refer to NHS talking therapies adult mental health services for support, and who at any stage of their NHS talking therapies journey, download and use any of the Wysa functionality.

The cCBT programmes will be accessed by a subset of the patients who are accepted for step 2 treatment. Step 2 treatment is usually offered to patients experiencing mild or moderate depression and/ or anxiety symptoms as recommended by NICE guidelines for stepped care in NHS talking therapies services.

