8.2.4.2 Secondary Outcomes

There will be several secondary outcome measures (see Table 6). The secondary outcomes will also be measured at both part 1 and part 2: e-triage, whilst waiting for treatment, during treatment and at discharge from treatment.

Patient Engagement

User engagement with Wysa will be assessed using a combination of complementary measures. Examining time spent using a digital health intervention is not by itself a reliable measure of effective engagement, as it cannot differentiate between users who spend a long time on the app because they're positively engaged compared to those who are frustrated and struggling to use it. Therefore, measures of app usage will also include uptake and dropout rates, and digital user feedback.

Patient experience

Wysa's acceptability will be examined through user score ratings (in app) out of a maximum of 5.

Health-related quality of life

Version number 1.1 - 25th November 2023

Work and Social Adjustment Scale [17] will be used to assess quality of life. The WSAS is a reliable measure for impairment in functioning and one of the NHS talking therapies standardised questionnaires. It provides a descriptive self-assessment of the impact of mental health difficulties in 5 dimensions: work, home management, social leisure, private leisure and personal or family relationships .

Secondary Outcome	Outcome Measure
Health related Quality of life	WSAS[17]
Patient Engagement	Referral rates Dropout / discharge reason/ did not attend rates App usage data
Patient experience	Automated review questions periodically requested during general use of the tool

Table 6. Secondary Outcome Measurements

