8.3.2 Sampling

8.3.2.1 Sample Size

All patients accepted by the NHS talking therapies services and meeting the inclusion criteria will be eligible for the study. A minimum of 100 patients will be recruited in order for the study to be able to conclude statistical validity. This is primarily a quantitative feasibility review with no control arm.

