8.5 Data Analysis

Descriptive and comparative statistics will be used to evaluate outcomes for those who use Wysa and those who do not, as well as clinical recovery, calculated by reduction in scores on the Standard NHS talking therapies measures as per NHS talking therapies guidelines [4]

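### Grouping patients by any Wysa use during the journey builds immortal-time bias into the drop-out comparison, in Wysa's favour

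*Protocol*

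**What the plan says.** The comparison is stated twice. Section 6 (Study Flow Chart) sets "patients who use Wysa throughout their NHS talking therapies journey, or for at least a part of their journey, with those who do not". Section 8.5 (Data Analysis) repeats it: "Descriptive and comparative statistics will be used to evaluate outcomes for those who use Wysa and those who do not".

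Section 7.4 lists as a secondary objective: "Do Wysa therapeutics improve service referral rates and/or reduce drop outs or DNAs". Table 6 in section 8.2.4.2 gives the measure as "Dropout / discharge reason/ did not attend rates", with no denominator.

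Section 6 names four points where Wysa can be used: referral, waitlist, step 2 intervention and post discharge. The download link goes out at referral; the cCBT programmes need a further link, sent once a clinician has judged them suitable. Section 8.1.1 says "the total time period for each participant journey will be approximately 20 weeks".

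The protocol does not say when follow-up for drop-out starts, or how a patient whose use begins partway through is classified before that point.

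**The concern.** Under an any-use rule, group membership depends on what happens after follow-up has begun. A patient who would have taken up the waitlist app in week 6 but leaves in week 3 is recorded as a non-user who dropped out. The same patient, had they stayed, would have been a user with six weeks of guaranteed retention behind them. The rule moves early drop-outs into one group and drop-out-free time into the other.

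This is separate from the question of who chooses Wysa. It arises even if would-be users and others have the same drop-out risk, so adjusting for baseline severity or obtaining complete records on non-users would not remove it. At stake is the drop-out objective: the study could report better retention with Wysa when there is none. Section 10.1 intends the results for publication and in support of regulatory approval.

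**Working it through.** **The plan's own figures.** There is none to reproduce for this objective. Section 8.3.2.1 says "A minimum of 100 patients will be recruited in order for the study to be able to conclude statistical validity" but gives no rates, effect size, alpha or power. The bias does not depend on that number.

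**Inputs.** From the protocol: journey of about 20 weeks; any-use grouping; first use possible after referral. Assumed, because the protocol is silent: 20-week drop-out D = 0.30 with constant hazard; share of would-be users q = 0.5; first use among them spread evenly over weeks 0 to W; no effect of Wysa; no difference in risk between would-be users and others.

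**Formulas.**
- Weekly hazard: L = -ln(1 - D)/20 = -ln(0.70)/20 = 0.01783.
- Share of would-be users who leave before first use: e = 1 - (1 - exp(-WL))/(WL).
- Drop-out in recorded users: (D - e)/(1 - e).
- Drop-out in recorded non-users: ((1 - q)D + qe)/((1 - q) + qe).

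**First use over weeks 0-12.** WL = 0.2140 and e = 0.0998.
- Users: (0.30 - 0.0998)/(1 - 0.0998) = 0.222.
- Non-users: (0.15 + 0.0499)/(0.50 + 0.0499) = 0.363.
- Gap: 14 points, with no true effect.

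**First use over weeks 0-4.** e = 0.0348.
- Users: 0.2652/0.9652 = 0.275.
- Non-users: 0.1674/0.5174 = 0.324.
- Gap: 5 points.

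**Some use at referral.** If half of the would-be users start at referral and the rest over weeks 0-12, e halves to 0.0499.
- Users: 0.2501/0.9501 = 0.263.
- Non-users: 0.1749/0.5249 = 0.333.
- Gap: 7 points.

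If all use starts at referral, e = 0, both groups show 0.30 and the gap is zero.

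**A second uptake model.** Here a share of all patients use Wysa at referral, and the rest start at a constant rate that would reach 60% by week 20 if nobody left. With 35% drop-out and no effect:

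| Using at referral | Users | Non-users | Ratio |
|---|---|---|---|
| 0% | 22.5% | 47.6% | 0.47 |
| 30% | 28.3% | 47.6% | 0.59 |
| 60% | 31.9% | 47.6% | 0.67 |

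The direction is the same and the size again depends on how much use starts at referral. When grouping is fixed at time zero, both groups show 35% (ratio 1.00).

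**DNAs.** These were simulated with 10 appointments, a true DNA probability of 10% unrelated to use, no use at referral and 60% uptake:
- one DNA ends care: 6.3% per appointment in users, 14.0% in non-users;
- two DNAs end care: 8.9% and 11.6%;
- DNAs never end care: 10.0% and 10.0%;
- DNAs never end care, patients leave for other reasons (4% chance after each appointment), counted per patient: 0.92 in users and 0.75 in non-users, which is against Wysa.

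The artefact can favour Wysa, vanish or reverse, depending on a denominator and a discharge practice that the protocol does not state.

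**The case against.** Several counter-arguments have force.

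- **Early access.** The link is sent at referral, and anyone who uses the e-triage or app then is a user even if they leave in week 1. This stands: it is wrong to infer that all early drop-outs become non-users. Early use shrinks the bias, but removes it only if no use starts later, and prescribed cCBT necessarily starts later.
- **Use after leaving.** A reader might infer that a user must, by definition, have been in the service at first use. The protocol does not support that: post-discharge use is a listed point of use, and nothing says the link lapses when a patient leaves. Such patients would be users who had already dropped out, which works against the bias and is a misclassification of its own. The calculations do not model it.
- **DNAs.** A reader might infer that DNAs will also appear to fall. The results above show that this does not follow.
- **Scope of the rule.** Section 8.2.1 refers to patients "who at any stage of their NHS talking therapies journey, download and use any of the Wysa functionality". That defines the target population and should not be read as the comparison rule, which rests on sections 6 and 8.5. Neither names drop-out, and section 8.3.2.1 says there is no control arm. Even so, both sections commit to comparing users with non-users, and the objective asks about a reduction, which needs a comparator.
- **Sampling.** Sections 8.3.2.2 and 8.3.3.1 limit entry to patients accepted into the service or onto step 2, so losses before acceptance are not sampled. Losses between acceptance and first use still are.
- **A SAP could set a time zero.** It could, but the point is not missing detail. The protocol states a grouping that misclassifies early leavers if followed.
- **Data on non-users.** Inclusion requires consent, and the opt-out information comes after download, so access to the records of patients who never download is not settled. That is a further difficulty and does not cure the timing bias.

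**Conclusion.** The concern holds for drop-out. Followed as written, the any-use grouping biases drop-out in Wysa's favour when use starts after referral among patients still in the service, which the protocol plainly allows. With 30% drop-out, 50% would-be users and no true effect, the gap is about 5 points (first use over weeks 0-4) to 14 points (weeks 0-12). Over 20-40% drop-out, 30-70% would-be users and both windows, the same formulas give about 3 to 24 points. None of these is a floor: the gap falls towards zero as use moves to referral. They illustrate size and do not predict it, since drop-out rate, uptake share and timing are all assumed.

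For DNAs no direction can be claimed. This is one exploratory secondary objective in a feasibility study, but the correction is cheap and should be made before the comparison is run.

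**What to change.** For the drop-out objective, replace any use during the journey with use fixed at a landmark:

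- Define the landmark, for example the sending of the download link, with the offer of cCBT as a separate landmark among patients offered it.
- Classify patients by use at the landmark or within a short fixed window after it (14 days, say).
- Include only patients still in the service when the window closes, and count drop-outs only from then.
- Ignore later or post-discharge first use in the grouping. Alternatively, treat use as time-varying, with each patient's time before first use counted as unexposed.
- If DNAs are compared, use DNAs per appointment booked after the landmark.
- State self-selection into Wysa as a remaining limitation.

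The cost is protocol wording and modest extra analysis. It needs dates of link sending, cCBT offer, first use and leaving the service; the protocol does not confirm that all are recorded, so this should be checked. Drop-outs inside the window leave the comparison, late starters count as non-users, and precision falls, which matters with about 100 patients and more than one landmark.

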8.2.3 Interventions

Wysa therapeutics include;

- An electronic triage, comprising of two parts:
 - a referral triage, comprising demographic information and some limited questions around physical health and past contact with mental health services
 - a clinical assessment triage, comprising a wide range of clinical questions and standardised outcome measures.
- Waitlist support;
 - 24/7 conversational care,
 - Access to over 150 self care tools
 - Daily check-ins to increase engagement and promote behavioural change.
- A range of diagnosis specific, NICE compliant therapist enabled step 2 cCBT programmes, delivered to patients via an app or widget. Each programme consists of 6-8 weekly modules, with each module focussing on a specific CBT principle or intervention. Psychoeducation is provided through short videos, with CBT techniques introduced in each video practised through conversational AI and augmented with self care audios and editable worksheets. The programmes also include the collection of standardised NHS talking therapies clinical outcome measures.

Wysa is delivered as a standalone system which patients download directly onto their personal device. Upon e-triage self-referral or alternative route referral to NHS talking therapies services the individual is automatically sent a download link via sms, email or QR code. Once downloaded, data from within the app, including outcome measures, tools used and crisis alerts are automatically pushed to the electronic patient record (iaptus) using the Mayden Prism software.

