8.2.4 Outcomes

8.2.4.1 Primary Outcomes

In order to understand the impact of Wysa therapeutics across the care pathway we will be conducting two distinct analyses. In Part 1 we will be focusing on e-triage and in Part 2 we will be focussing on the waitlist support and cCBT programmes.

The primary analysis in Part 1 will be a comparison of the time spent by the clinician to make a decision on the treatment pathway for those who complete the Wysa e-triage, with that taken to make a decision for patients who do not. The primary outcome measure will be time taken for the clinician to make a decision, for each of these two assessment pathways.

The primary analysis in Part 2 will be a comparison of depression and anxiety scores before and after a Wysa intervention (waitlist self care or step 2 cCBT). The primary outcomes will be measured at onboarding, start of intervention and discharge from intervention. In line with the national recommendations laid out by the NHS talking therapies Manual, we will be using Wysa's AI automation to encourage users to complete the Patient Health Questionnaire (PHQ-9 [15) and General Anxiety Disorder (GAD-7 [16]) routine outcome measures.

	Primary Outcome	Outcome Measure
Part 1: E-triage	Clinical Time Savings	Hours/Minutes
Part 2: Waitlist and cCBT	Depression or Anxiety severity	Score on the PHQ9 and GAD7

Table 5. Primary Outcome Measurement

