8.3.2.2 Sampling Technique

Part 1: Participants will be all patients who self-refer or are referred to an NHS talking therapies service and accepted into the service.

Part 2: Participants will be patients who are accepted onto the Step 2 waiting list and consent to digital treatment.

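### The Part 1 time comparison sets e-triage, described as a self-referral route, against a comparator that also takes in professional referrals, so the time saving may partly reflect referral route

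*Protocol*

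**What the plan says.** **How patients reach the e-triage.** Section 6 (Study Flow Chart) describes entry to the pathway as "Following self-referral (either using the Wysa electronic triage tool or another method such as self referral portal or email) or professional referral". The e-triage sits inside the bracket that lists methods of self-referral; professional referral stands outside it. Section 8.2.3 makes the same split: "Upon e-triage self-referral or alternative route referral to NHS talking therapies services".

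**What the tool is.** Section 6 also says that "Wysa will be made available to patients as a self referral and clinical triage tool". Section 8.2.3 divides the e-triage into a referral part and a clinical assessment part, and ties no referral route to the second.

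**Who is in Part 1.** Section 8.3.2.2 states: "Part 1: Participants will be all patients who self-refer or are referred to an NHS talking therapies service and accepted into the service". Section 8.3.3.1 identifies participants in the same way.

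**What is compared.** Section 8.2.4.1 compares clinician time "for those who complete the Wysa e-triage, with that taken to make a decision for patients who do not", and adds: "The primary outcome measure will be time taken for the clinician to make a decision, for each of these two assessment pathways". Table 5 labels this outcome as clinical time savings, in hours and minutes.

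**Design and analysis.** Section 8.3.2.1 describes a feasibility review without a control arm and a minimum of 100 patients. Section 8.5 announces descriptive and comparative methods for users against non-users and does not mention referral route.

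**The concern.** Referral route is settled before a patient can start the e-triage, and it may affect how long a clinician needs. A professional referral may concern a more complex case and take longer, or it may arrive with information that shortens the decision. If one group contains only self-referrals and the other a mixture, the difference in mean decision time carries both the tool's effect and the effect of route, and a reader cannot separate them.

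This bears on the primary outcome of Part 1. The difference will be read as time saved by the tool, and Section 10.1 intends the data to support regulatory approval and wider adoption. Without randomisation, nothing in the design balances route between the groups. Here the imbalance comes from the way the groups are defined, so wording can remove it.

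**Working it through.** The protocol gives no figure for decision time, for the mix of referral routes or for the Part 1 group sizes. The minimum of 100 comes without alpha, power, effect size, SD or split, so it cannot be reproduced, and the point does not depend on it. The check is mainly one of reading.

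**Step 1: who can be in each group.**

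| Referral route | E-triage completers | Comparator (non-completers) |
|---|---|---|
| Self-referral through e-triage | Yes (Sections 6, 8.2.3) | No |
| Self-referral by portal, email or other method | None described | Yes (Section 8.2.4.1) |
| Professional referral | None described | Yes (Sections 8.3.2.2, 8.2.4.1) |

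Professional referrals do stay in the study. Section 6 gives the app link after any type of referral, and Section 8.4.1 provides for patients who skip the e-triage by measuring them when they onboard the app.

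**Step 2: the artefact as a formula.** Let *d* be the mean decision time for professional referrals minus that for self-referrals. Let *q* be the share of professional referrals in the comparator and *e* their share among e-triage completers. If *d* is the same in both groups and the tool has no effect, the apparent saving is

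(q − e) × d.

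On the plain reading of Step 1, e = 0, so the artefact is q × d. It shrinks as *e* approaches *q*.

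**Step 3: illustration.** Every input here is an assumption: e = 0; q of 10%, 25% or 50%; d of 5, 10 or 20 minutes; 50 patients per group; within-route SD of 15 minutes; two-sided 5% test with a normal approximation. The comparator variance is 15² + q(1 − q)d², and SE = √(15²/50 + comparator variance/50). The chance of a significant result in favour of a tool with no effect is Φ(qd/SE − 1.96).

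| q | d = 5 min | d = 10 min | d = 20 min |
|---|---|---|---|
| 10% | 0.5 min; 3.6% | 1.0 min; 5.2% | 2.0 min; 9.4% |
| 25% | 1.25 min; 6.1% | 2.5 min; 12.6% | 5.0 min; 33.8% |
| 50% | 2.5 min; 12.9% | 5.0 min; 36.8% | 10.0 min; 85.4% |

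The nominal chance in that direction is 2.5%. For the last cell: comparator variance 225 + 0.25 × 400 = 325; SE = √(225/50 + 325/50) = √11 = 3.32; 10/3.32 − 1.96 = 1.05; Φ = 0.854. If professional referrals take less time, *d* is negative and the artefact hides a real saving instead.

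**Step 4: can analysis repair it?** Stratifying or adjusting for route needs patients of each route in both groups. If e = 0, the professional-referral stratum has no e-triage patients, and a model could only extrapolate there. If *e* is above zero, route is an ordinary baseline imbalance that stratification or adjustment can handle.

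**The case against.** The best counter-argument is that the e-triage is more than a referral form. Section 6 calls Wysa a clinical triage tool as well and describes it as offered to every patient with a suitable device. The clinical assessment part in Section 8.2.3 has no route attached, and it is the part that would most directly stand in for the clinician's assessment. The flow figures, where such access might be drawn, are not available here. This stands in part. A reader might infer that professionally referred patients can never complete the e-triage and that no adjustment could repair the comparison. The documents do not support so strong a reading: they are silent on the matter and do not bar access. Equally, none of the text grants it, and what Section 6 describes for patients after referral is the app link, not the e-triage.

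A second objection is that an SAP could adjust for route or restrict the analysis set. It could. But the population and the comparator are fixed in the protocol, and adjustment helps only if the routes overlap.

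Third, the illustration takes nothing from the documents. That is correct. At its low end (0.5 minutes; 3.6% against 2.5%) the effect is negligible, and the 85.4% needs the most extreme pairing. The table shows how the artefact scales; it is not evidence that the artefact is large.

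Finally, patients choose whether to use the e-triage, and that self-selection is probably the broader threat to Part 1. The point about route does not remove it, but route is a separate source of difference and is avoidable.

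**Conclusion.** The point holds in a conditional form. On the protocol's wording, professional referrals appear to fall wholly or mainly in the Part 1 comparator, so the primary time difference may partly reflect referral route. Its size and direction cannot be found from the documents; the range of 0.5–10 minutes rests entirely on the assumed shares and time differences. If professional referrals have no access to the e-triage, adjustment for route would have no overlap to work with. If they do have access, the problem is ordinary confounding, which comparison within route would address. Confidence is moderate, because access to the clinical assessment part is not stated. This is a cheap improvement, not a flaw that invalidates Part 1.

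**What to change.** - In Sections 8.2.4.1 and 8.3.2.2, define the primary Part 1 comparison as patients who self-refer through the e-triage versus patients who self-refer by portal, email or another method and then have the standard assessment.
- Report decision time for professional referrals separately and descriptively.
- State whether professionally referred patients can complete the clinical assessment part of the e-triage. If they can, say so and compare decision time within referral route.

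**Cost.** The change is one of wording, provided that referral route is recorded for each patient; the protocol does not say that it is, and the sponsor must confirm it. The comparator for the primary contrast becomes smaller, with a loss of precision that cannot be calculated without the mix of routes. Self-selection among self-referrers remains and should be acknowledged when the result is interpreted.
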